15.4.2 Secondary Analyses

As a secondary analysis, ondansetron dose level, prior use of methamphetamine in the last 30 days (≤ 10 and > 10 days), age of onset of methamphetamine use (≤ 17 years of age versus > 17 years old), gender, diagnosis of ADD, alcohol use (average number of drinks per day in last 30 days determined by timeline followback) and their first-order interactions with treatment will also be included in the model. Presentation will include the full model with all terms and a reduced model containing only significant terms.

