ANALYSIS: Each primary and secondary outcome variable will be analyzed using appropriate statistical methods for the intent-to-treat population and for the evaluable population. The intent-to-treat population is defined as the subjects who are randomized and receive the first day's study agent. The evaluable population is defined as the subjects who are randomized, meet the inclusion and exclusion criteria and who contribute at least four (4) usable on-study urine samples and 21 days of self report of methamphetamine use/non-use reported on a substance use report (SUR). The individual effects, if any, of ondansetron dose level, age of onset of methamphetamine use (early onset, ≤ 17 years of age, versus late onset, > 17 years of age), frequency of methamphetamine use (current high, > 10 days versus low, ≤ 10 days of use in the last 30 days determined by timeline followback during screening), gender, diagnosis of ADD, alcohol use (average number of drinks per day in the last 30 days determined by timeline followback during screening), and their first-order interactions on the primary treatment effects will be determined where numbers permit. No attempt will be made to determine the effect of two or more of these variables acting together. Statistical tests will be two-sided at a 5% Type I error rate. Confidence intervals will be two-sided with a 95% confidence coefficient.

Summaries of the characteristics of the subject population in each treatment arm at baseline will be prepared for both the intent-to-treat and evaluable subjects. A summary will be prepared to show dropouts/retention over time in each treatment group. The number of missing observations will be compared between treatments. Weekly treatment compliance will be summarized. All adverse events will be reported in tabular form indicating the frequency of each type of event. Dose-response and concentration-response curves will be generated to determine the optimal effective dose with minimal side effects.

BACKGROUND AND RATIONALE

4.1 **METHAMPHETAMINE**

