8 STUDY DESIGN

8.1 EXPERIMENTAL DESIGN

This is a double-blind, placebo-controlled, randomized, four arm dose-ranging study comparing three dose levels of ondansetron (0.25, 1.0, and 4.0 mg, b.i.d.) to placebo administered to methamphetamine dependent outpatients. Randomization strata include investigational site, age of onset of methamphetamine use (early onset, \leq 17 years of age, versus late onset, > 17 years of age), and frequency of methamphetamine use (current high, > 10 days versus low, \leq 10 days of use in the last 30 days). All subjects will receive a base of standardized, manual-driven CBT (a 90 minute group session three times per week) over 8 weeks of treatment (Huber *et al.*, 1997, Rawson *et al.*, 1995, Shoptaw *et al.* 1994). A final follow-up assessment will be conducted 4 weeks after completion of treatment.

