15.4 ANALYSIS PLAN

15.4.1 Efficacy Assessments

Each primary and secondary efficacy outcome measure will be analyzed for the intent-to-treat and for the evaluable population. Major differences in the results, if any, will be further explored. While there is every intent to be complete in describing the analyses to be performed, it is not possible to anticipate every contingency and some adjustments may be required to meet constraints posed by the structure of the data.

All statistical tests will be two-sided at a 5% Type I error rate. Confidence intervals will be two-sided with a 95% confidence coefficient.

Primary Efficacy Outcomes

The weekly mean proportion of methamphetamine-free urines on study will be compared between treatment groups using Generalized Estimating Equations (GEE) for ordinal categorical response (Lipsitz *et al.*, 1994). GEE provide a model-based regression method applicable for the analysis of the correlated data that will result from this repeated measures longitudinal study. The GEE procedure was first proposed by Liang and Zeger (1986) and Zeger and Liang (1986) and models the population average. GEE has several useful features:

- 1. It can be used to analyze different types of outcomes such as continuous, binary, or count.
- 2. It can be used to analyze an unbalanced design caused by either differing numbers of observations per person or by observations taken at different times.
- 3. The parameter estimates are consistent even if assumptions about the variance structure are not completely accurate.

Secondary Efficacy Outcomes

Unless the primary response analysis implies the need for a more elaborate model, between group comparisons of the secondary outcomes will be performed as follows:

Outcome Measure	Test
A, C, G, I, J	Chi-square tests
D, E, G, L, Q	Analysis of Variance
B, F, H, K, L, M, N, O, P	GEE
R	Wilcoxon (Gehan)

S. Adverse events, laboratory data, physical exams, and vital signs will be reported in tabular form. AEs will be listed indicating the frequency of each type of event. The frequencies of adverse events by type will be compared between study arms using Chi-square analyses.

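### Section 15.4.2 specifies a dose-by-treatment interaction that cannot be estimated and a significance-selected reduced model without valid p-values or intervals; separately, five unadjusted interaction tests carry about a 23% chance of a false modifier

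*Protocol*

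**What the plan says.** Section 8.1 describes a four-arm trial "comparing three dose levels of ondansetron (0.25, 1.0, and 4.0 mg, b.i.d.) to placebo".

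Section 15.4.2 opens with "As a secondary analysis, ondansetron dose level, prior use of methamphetamine in the last 30 days" and goes on to age of onset, gender, ADD diagnosis and average daily drinks. It then states that "their first-order interactions with treatment will also be included in the model". Read literally, that is six interactions: dose level by treatment, and five baseline modifiers by treatment. On reporting: "Presentation will include the full model with all terms and a reduced model containing only significant terms".

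Section 15.4.1 fixes the error level: "All statistical tests will be two-sided at a 5% Type I error rate". It sets confidence intervals at 95% and states no adjustment for the number of interactions.

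The analysis paragraph of the Protocol Synopsis covers the same variables, "and their first-order interactions on the primary treatment effects will be determined where numbers permit", and adds: "No attempt will be made to determine the effect of two or more of these variables acting together".

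Section 5.1 calls the trial a preliminary assessment whose results will be used to design larger confirmatory studies. It also says the study is meant to collect preliminary information on patients who may respond better. Section 16.3 says the analysis will follow the protocol's own analytical plan.

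**The concern.** There are three separate problems.

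1. Dose level is listed as a covariate that interacts with treatment, yet in this design dose is what distinguishes the treatment arms. One specified term therefore has no information behind it. The protocol also does not say whether treatment in this model means the four arms or active versus placebo. That choice decides whether each modifier interaction has three degrees of freedom or one.

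2. A model containing only the terms that reached significance has been chosen by the same data that then supply its p-values and intervals. Those no longer mean what section 15.4.1 says they mean.

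3. Five modifiers are each tested at the full 5%, in a trial that hopes to learn who responds. A modifier that appears by chance could shape the eligibility or stratification of the next study.

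**Working it through.** **The plan's own figure.** Section 15.5 gives no effect size, power or error rate for the secondary model. Its one calculation is 30 evaluable per arm with 30% not evaluable: 30 / (1 − 0.30) = 42.9, so 43 per arm. The protocol uses 45 per arm and 180 in total, which fits rounding up. The model would therefore be fitted to about 4 × 30 = 120 evaluable or 180 randomized subjects.

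**Can dose level by treatment be estimated?** Placebo has dose 0 and each active arm has one dose, so there are only four distinct combinations. Three codings were checked on 4 × 45 subjects:

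| Coding of treatment and dose | Rank with treatment only | Rank with dose added | Rank with dose × treatment added | Columns in last model |
|---|---|---|---|---|
| Four-arm factor, linear dose | 4 | 4 | 4 | 8 |
| Active/placebo, linear dose | 2 | 3 | 3 | 4 |
| Active/placebo, categorical dose | 2 | 4 | 4 | 8 |

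The interaction never raises the rank. In the second row the reason is plain: dose is zero under placebo, so the active indicator multiplied by dose is the dose column again. That row also shows that a dose main effect can be estimated if treatment means active versus placebo.

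**Chance of a false modifier.** Removing dose level by treatment leaves five interactions. With no true interaction and independent tests at 5% each:

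1 − 0.95^5 = 0.226.

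This holds whether each test has three degrees of freedom or one. With a four-level treatment factor the model has 1 + 3 + 5 + 15 = 24 parameters.

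**How much does the reduction add?** A null simulation was run with 1,500 runs per setting and 45 or 30 subjects per arm. It used one normal outcome per subject in place of the weekly ordinal outcome, four binary modifiers with assumed prevalences of 25% to 50%, and a skewed alcohol variable. Backward elimination was at 5%, with treatment kept in and main effects kept under their interactions. With model-based variance:

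| Setting | Any interaction significant, full model | Any interaction retained, reduced model |
|---|---|---|
| Four-arm factor, 45 per arm | 21.5% | 22.2% |
| Four-arm factor, 30 per arm | 21.3% | 23.9% |
| Active/placebo plus dose, 45 per arm | 21.3% | 23.4% |
| Active/placebo plus dose, 30 per arm | 22.1% | 23.7% |

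Reduction adds about 1 to 3 percentage points. With an uncorrected sandwich variance the full-model figure was higher (33% to 56%), and reduction did not raise it further.

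**What the reduction does spoil.** In every setting, 100% of retained interactions had p < 0.05 although all were null; with model-based variance the median was about 0.024. A 95% region that goes with p < 0.05 excludes zero, so among retained terms none of these regions covered the true value.

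**After correction.** Testing each of the five at 0.05 / 5 = 0.01 gives 1 − 0.99^5 = 4.9% if independent and at most 5% in general. Holm keeps the same bound with somewhat more power.

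**The case against.** The strongest reply is that this is a secondary analysis in a pilot study that calls its responder information preliminary, and that nothing is hidden because the full model is shown too. Much of that stands, and several stronger readings fail because of it.

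- A reader might infer that the model is cut down and only the reduced version is used. The protocol presents both and does not make the reduced model the basis for inference. Full-model p-values are not distorted by selection, only unadjusted for multiplicity.
- A reader might attribute the 23% to the reduction. It is the error rate of five unadjusted tests with no selection at all.
- A reader might quote a chance near one half. Reading the 15 dose-specific terms one by one gives 1 − 0.95^15 = 53.7% if independent and 48% to 49% in the simulation. But section 15.4.2 does not say they will be read that way.
- A reader might say dose level can have no place in the model. That is true only if treatment means the four arms. Software usually drops a redundant term, and this need not bias the rest.
- A reader might see the synopsis as contradicting section 15.4.2. The synopsis does provide for first-order interactions, subject to numbers. Its sentence on variables acting together can be read as excluding combinations of modifiers, which section 15.4.2 does not add.
- A reader might fear for the efficacy result. The primary comparison is a separate GEE analysis in section 15.4.1, and no section takes the efficacy estimate from the reduced model.

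Section 15.4.1 also allows adjustments forced by the structure of the data. That does not answer the first problem, because the redundancy lies in the design and is known before any data exist.

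**Conclusion.** The point holds in a limited form. Section 15.4.2 states one interaction that no coding can estimate, and one reporting rule whose p-values and intervals do not have their nominal level. Neither conclusion depends on the simulation. Apart from these, the five remaining interactions carry about a 22–23% chance of at least one false modifier when none exists, against a nominal 5% per test.

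The 22.6% assumes independent tests that each hold their 5% level. The simulated 21–24% rests on a normal stand-in for the ordinal GEE and on assumed modifier distributions, because the protocol gives none. The sandwich-variance results suggest that real GEE tests could exceed 5% each at this size, but the stand-in cannot settle by how much.

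The consequence is confined to the responder information described in section 5.1. The primary efficacy comparison is not affected.

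**What to change.** In section 15.4.2:

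1. Define treatment and dose once, as a single four-level factor (placebo and the three doses), and delete dose level by treatment.
2. Drop the reduced model, or present it as descriptive only, without p-values or intervals.
3. Report all five modifier interactions, one three-degree-of-freedom test each, with intervals whether or not they are significant.
4. Either apply Holm across the five tests (familywise error at most 5%, provided each test holds its own level), or state the error rate of about 23% and label the results hypothesis-generating. Moving to five single tests without this step would leave the 22.6% unchanged.

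The synopsis paragraph and the covariate list in section 8.2, which also name dose level, should be aligned. The change affects analysis wording only and has no operational cost. The downside is lower power for each single interaction if Holm is chosen.

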15.4.3 Dose Response Analysis

Dose response curves will be generated using the slope of the GEE for the primary outcome measure. The frequency and severity of adverse events will be presented for each dose. The shape and the location of the population (group) average dose response will be evaluated for positive outcomes and adverse events to select the best dose for larger phase 2 studies.

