4.8 ONDANSETRON DOSE JUSTIFICATION

This is a dose-ranging study because high doses of ondansetron (8 mg 2 or 3 times per day) are recommended and currently used to prevent nausea and vomiting associated with emetogenic chemotherapy, but much lower doses were found effective for the treatment of alcohol dependence. This study will explore three doses of ondansetron 0.25, 1.0, and 4.0 mg, to be taken orally twice per day (b.i.d) for the 8 weeks of treatment.

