15.2 STATISTICAL HYPOTHESES

15.2.1 Primary Efficacy Outcome

It is hypothesized that ondansetron as compared to placebo will decrease the weekly proportion of methamphetamine positive urine specimens over the treatment period.

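### The dose-response curve is to be built from an undefined GEE slope that cannot show a plateau or interior optimum, and neither the primary contrast nor the primary population is fixed

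*Protocol*

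**What the plan says.** - **Design (section 8.1):** "four arm dose-ranging study comparing three dose levels of ondansetron (0.25, 1.0, and 4.0 mg, b.i.d.) to placebo".
- **Hypothesis (section 15.2.1):** "It is hypothesized that ondansetron as compared to placebo will decrease the weekly proportion of methamphetamine positive urine specimens over the treatment period". It is not written dose by dose.
- **Primary analysis (section 15.4.1):** treatment groups are compared by GEE for an ordinal response. Whether this is an omnibus, a pooled or a dose-by-dose comparison is not stated. Section 15.4.2 then lists dose level as a term in a secondary model.
- **Error rate (section 15.4.1):** "All statistical tests will be two-sided at a 5% Type I error rate".
- **Populations (section 15.4.1):** "Each primary and secondary efficacy outcome measure will be analyzed for the intent-to-treat and for the evaluable population". Neither is called primary. Section 15.3 defines the evaluable set by at least four usable on-study urines and 21 days of self-report, that is, by attendance after randomization.
- **Dose-response (section 15.4.3):** "Dose response curves will be generated using the slope of the GEE for the primary outcome measure". The same section goes on to evaluate the shape and location of the group-average response, for benefit and for adverse events, in order to choose a dose for larger studies.
- **Prior evidence on dose (section 4.8):** "much lower doses were found effective for the treatment of alcohol dependence".

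**The concern.** Choosing a dose is a stated deliverable of this trial, yet the quantity that produces the curve does not fit that purpose. One slope over dose is a straight line on whatever scale is used. It has a direction and a steepness but no shape, so it cannot supply the shape that section 15.4.3 wants evaluated. A slope over weeks describes the rate of change, whereas the primary outcome is the level of use across the eight weeks.

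The shapes that would be lost are ones the protocol gives reason to expect. Section 4.5 reports benefit in early-onset alcohol dependence at 1, 4 and 16 µg/kg. Section 4.6 equates 64 µg/kg with 4.48 mg per 70 kg, so those doses are about 0.07, 0.28 and 1.12 mg. They cover the range of the low and middle arms, not the 4 mg arm.

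Separately, with no primary contrast and two unranked populations, the stated 5% does not attach to any single efficacy claim.

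**Working it through.** **Inputs from the protocol.** Doses 0, 0.25, 1 and 4 mg; four arms; 30 evaluable and 45 randomized per arm (section 15.5); two-sided 5%. The plan gives no power and no familywise rate. Its one related figure is the inflation for non-evaluable subjects: 30/0.70 = 42.9, so 43 would suffice, and the planned 45 gives 45 × 0.70 = 31.5. The evaluable fraction is therefore about 0.67 (30/45) to 0.70.

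**Assumptions.** The protocol gives no effect size. I use a maximum effect of 0.6 SD on the week-averaged outcome, with a range of 0.4 to 0.8 SD, equal arms, unit SD and normal theory.

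**1. Slope over dose.** Let c be the centred dose scores scaled to unit length, m the shape of the true effect (maximum 1), e the effect in SD and n the number per arm.
- Slope test: λ = e√n · Σcm; power = Φ(λ − 1.96) + Φ(−λ − 1.96).
- 3-df test: noncentrality = n e² Σ(m − mean m)².
- In mg the centred doses are −1.3125, −1.0625, −0.3125 and 2.6875, with sum of squares 10.17. The 4 mg arm carries 7.22/10.17 = 71% of the leverage. With log(dose + 0.25) it carries 53%, and with rank scores 45%.
- Example, plateau from the lowest dose, mg scale, n = 30: λ = 0.6 × 5.477 × 0.412 = 1.35, power 27%. For the 3-df test: 30 × 0.36 × 0.75 = 8.10, power 66%.

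Rejection rate (%) at 30 per arm, for 0.6 SD (0.4 to 0.8 SD):

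| True shape | 3-df test | Slope, mg | Slope, log | Slope, rank |
|---|---|---|---|---|
| Plateau from 0.25 mg | 66.0 (32.5–90.5) | 27.2 (14.7–43.8) | 51.1 (26.3–75.5) | 59.7 (31.2–83.6) |
| 1 mg only | 66.0 (32.5–90.5) | 6.2 (5.5–7.1) | 8.0 (6.3–10.3) | 11.4 (7.8–16.5) |
| 0.25 mg only | 66.0 (32.5–90.5) | 19.5 (11.3–30.9) | 15.0 (9.4–23.0) | 11.4 (7.8–16.5) |
| Linear in mg | 58.0 (27.9–84.7) | 74.5 (41.6–93.7) | 69.4 (37.7–90.8) | 64.9 (34.5–87.8) |

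For an effect at 0.25 mg only, Σcm is −0.333 (mg), −0.278 (log) and −0.224 (rank). The expected slope has the wrong sign on every scale, so most of those rejections point the wrong way. For 1 mg only, the sign is wrong on the mg scale (−0.098).

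At 45 per arm and 0.6 SD the 3-df test has 84.5% for the first three shapes. The slope has 38.1/68.3/77.0% (mg/log/rank) for the plateau and 6.8/9.5/14.7% for 1 mg only.

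**2. Slope over weeks.** If the difference from placebo is δ in each of weeks 1 to 8, the week-averaged difference is δ and the difference in weekly slope is 0, whatever the size of δ.

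**3. False-positive risk under no effect at any dose.** Dose-placebo statistics share the placebo arm (correlation 0.5). The evaluable set is treated as a random 67–70% subset of intent-to-treat. Results are by numerical integration and by 2 million simulated trials.

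| Decision rule | One set | Either set |
|---|---|---|
| One 3-df omnibus test | 5.0% | 7.7–7.9% |
| Three dose-placebo tests, any error | 12.5% | 18.5–18.8% |
| Three dose-placebo tests, errors favouring ondansetron | 6.3% | 9.2–9.4% |

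With larger evaluable fractions the 18.5–18.8% falls, to 17.4% at 0.80 and 15.9% at 0.90.

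**The case against.** A reader might infer that the doses are each tested against placebo at 5%, so that the false-positive risk is simply 13–18%. The protocol does not say this. Its wording fits an omnibus or a pooled test equally well, and the higher figures hold only under pairwise testing. The two-set figures further need a rule that either set may carry the claim, whereas section 15.4.1 says only that major differences between the sets will be explored, which can be read as a consistency check.

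A reader might also infer that the dose is chosen from one slope alone. Section 15.4.3 contradicts that: shape, location and adverse events all enter. It describes curves and a judgement, not a slope test, so the power figures measure how much information a slope retains and are not the power of a planned test. The mg scale is also the least favourable one for a plateau. With log or rank scores the loss is much smaller (51% or 60% against 66%), though the single-dose shapes stay poor on every scale.

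Finally, this is a pilot whose results are to be confirmed in larger studies, and an analysis plan may exist that settles the contrasts.

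What stands of this: the error rates must be stated conditionally, and the pilot status lowers the weight of the multiplicity point. What does not: promising to evaluate shape does not help if the curve is generated from a quantity that contains none. Nor are these matters deferred, since section 16.3 says the analysis will follow the protocol's own analytical plan section.

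**Conclusion.** The point holds in this form. The slope in section 15.4.3 is undefined. As a single slope over dose it conflicts with the section's own aim of evaluating shape. As a slope over weeks it does not measure the primary outcome. The loss is modest for a plateau on a log or rank scale, large for a plateau on the mg scale, and near-total for an effect at one low or middle dose. These sizes rest on the assumed 0.6 SD and normal theory; the ordering of the 3-df test over the slope for these shapes is the same across 0.4–0.8 SD. If slope was meant loosely, for a set of dose-specific coefficients, the text should say so and this part of the point is met.

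The missing primary contrast and primary population are a second, lesser defect. The risk ranges from 5% to about 19% depending on a rule the protocol does not state.

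**What to change.** In sections 15.4.1 and 15.4.3, before unblinding:

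1. Make the intent-to-treat set primary and the evaluable set a sensitivity analysis.
2. Enter dose in the GEE as a four-level factor.
3. Make one test of the week-averaged effect primary at two-sided 5%, for example the 3-df test.
4. Label the dose-placebo comparisons as supportive, or adjust them.
5. Draw the dose-response curve from the dose-specific week-averaged estimates with intervals, in place of a slope. The judgement on shape, location and adverse events can then proceed as section 15.4.3 intends.

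**Cost.** Wording only, with no added subjects or visits. If the response is truly linear in mg, power falls from 75% to 58% at 30 per arm under the assumed effect (89% to 78% at 45). If Dunnett adjustment is chosen, intervals widen by about 20% (2.349/1.960 = 1.20), and power for a single 0.6 SD dose-placebo comparison falls from 64% to about 49% at 30 per arm, or from 81% to about 69% at 45. Leaving those comparisons unadjusted but labelled supportive avoids that loss. Which of the two to use is a reasonable choice for the sponsor in a pilot.
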